2.3.1 Risks shared by both DFV890 and MAS825

2.3.1.1 Potential risk and recommended treatment of infection

As with any immune-modulating compound, there is a theoretical risk of immune system impairment, which might increase risk of infection in treated participants.

However, DFV890 is not expected to elicit broad immune suppression. Moreover, the target NLRP3 is not essential for health (NLRP3 deficient mice are viable and fertile). **CCI**

[REDACTED]

[REDACTED] These findings were not seen in a previous 13-week toxicology monkey study, which had higher systemic exposures.

Similarly, MAS825 is not expected to elicit broad immune suppression, rather selectively neutralize the pro-inflammatory IL-1 β and free/bioactive IL-18.

The risk for patients in currently ongoing trials is considered low based on safety margins and/or short treatment duration. To mitigate potential risks of immune suppression and infection in this study, immune suppressive treatments are prohibited to be administered 28 days or 5 half-lives, whichever is longer, prior to screening and concurrent use of these treatments is also prohibited. Participants with known or suspected immunodeficiency state or evidence of active or latent, serious bacterial, fungal or viral infections will also be excluded. See [Section 5.2](#).

In response to the COVID-19 pandemic, site-specific procedures should be implemented to minimize COVID-19 infection risks for participants and site staff as per local guidance. These documents may cover, but are not limited to, local COVID-19 testing, infection prevention/control, hygiene and social distancing measures. Investigator must instruct participants to contact the investigator immediately if the participants develop any symptoms and/or signs of infection (e.g., fever, loss of smell, loss of taste, muscle aches, persistent or productive cough, abdominal pain, vomiting, nausea, shortness of breath, dysuria and/or diarrhea).

In the event of an infection, investigators should consider early treatment with specific antimicrobial therapy based on clinical diagnosis or suspicion thereof (e.g., prompt antibiotic therapy for bacterial infections, anti-viral treatment for herpes simplex or zoster or SARS-CoV-2, etc.) in consultation with infectious disease experts, as appropriate.

2.3.1.2 Potential risk and guidance on vaccinations

To mitigate the risk from live vaccinations, participants who have received live vaccinations within one month prior to the first dose of the study will be excluded from entry in this study. Additionally, it is recommended that all participants should complete all immunizations in accordance with current immunization guidelines at least one month prior to administration of the first dose (Day 1).

Approved (including Health Authorities' conditional marketing authorization) killed, inactivated, peptide, DNA and RNA vaccines are permitted according to the investigator's discretion and per local guidance. Due to the mechanism of action of DFV890 and MAS825, specifically targeting the NLRP3 inflammasome or downstream cytokines IL-1 β and IL-18, it is unlikely that treatment with this compound would interfere with vaccination responses. However, no specific preclinical nor clinical investigations of vaccine efficacy have been conducted to date with DFV890 or MAS825.

2.3.1.3 Potential risk and recommended monitoring of hematological parameters

For DFV890, transient asymptomatic decreases in absolute neutrophil count (ANC) and white blood cell (WBC) were observed in the CDFV890A02101 FIH and CDFV890D12201 COVID-19 studies. These transient self-limiting decreases in ANC and WBC were not associated with an increased risk of infection which could be consistent with a PD effect of DFV890 resulting from inhibition of IL-1 β signaling downstream of NLRP3 (NLRP3 blockade, similar to known effects of canakinumab).

For MAS825, transient decreases in WBC and ANC may also occur with mAb inhibition of IL-1 β as seen in the CANTOS study with canakinumab. In addition, transient decreases in platelet counts were observed following canakinumab treatment of inflammatory disorders, and dose-dependent decreases in platelet counts were observed in small numbers of patients in CANTOS. Based on the safety data available from the canakinumab clinical trials program, no correlation between reduced platelet counts and bleeding has been identified.

As a precaution, all patients with suspected or known immunodeficiencies will be excluded from this study. In addition, patients with cytopenias (such as persistent neutropenia (ANC < 1.8 \times 10⁹/L), and/or thrombocytopenia (platelets < 150 \times 10⁹/L)) will also be excluded from entry into this study (see [Section 5.2](#)). Complete blood counts will be monitored in this study. Subjects should be alert for the appearance of symptoms (bleeding from gums or nose) and signs of thrombocytopenia (purpura, petechiae, ecchymoses). Investigators should consider treatment of severe thrombocytopenia (<50 \times 10⁹/L) based on clinical assessment and/or evidence of bleeding in consultation with a hematologist, as appropriate.

2.3.1.4 Potential risk and recommended treatment of hypersensitivity reactions

Treatment with DFV890 is contraindicated in people with hypersensitivity to any component of the drug product.

As with most biologic compounds, administration of MAS825 carries the risk of anaphylaxis and/or hypersensitivity-type reactions. In the event of such a reaction, treatment with antihistamines and glucocorticoids may be considered, as clinically indicated. Depending on severity, patients may also require supplemental oxygen, volume expansion, catecholamines, and transfer to an intensive care setting. Plasmapheresis to decrease the systemic concentration of MAS825 may be considered dependent on the patient's condition. Patients should be observed for at least four hours after resolution of signs and symptoms, and those who have experience severe infusion reactions should be closely observed for 24 hours after resolution because of the risk of a biphasic episode. Based on the clinical experience to date with MAS825, CCI [REDACTED] (CCI [REDACTED], anti-IL-1 β mAb component), and CCI [REDACTED] (anti-IL-18 mAb component), the risk of a hypersensitivity reaction is considered low.

2.3.1.5 Potential risks and guidance related to WOCBP

At this stage of development, DFV890 has not yet been studied in reproductive toxicology studies, and WOCBP and sexually active males must be informed that taking the study treatment may involve unknown risks to the fetus if pregnancy were to occur during the study, and agree that in order to participate in the study they must adhere to the contraception requirements outlined in the exclusion criteria. Based on an *in vitro* induction of CYP3A4, there is a slight potential risk for a drug-drug interaction (DDI) of DFV890 with hormonal contraception at high exposures, therefore oral hormonal contraception is allowed, but must be supplemented with a barrier method, preferably a male condom. If there is any question that the participant will not reliably comply, they should not be entered or continue in the study.

There is no available reproductive toxicity data for MAS825 nor clinical experience with the mAb in human pregnancies. CCI to other CCI antibodies, MAS825 may have CCI cross-placental transfer. The potential of placental transfer can be influenced by many factors (maternal level of the total CCI specific antibodies and their subclasses, gestational age and placental integrity) (Palmeira et al 2012).

Thus, WOCBP can be included if they fulfill the following criteria:

- Practice highly effective contraception for at least 1 month prior to screening;
- Have a negative pregnancy test at the time of screening; pregnancy tests at each treatment visit, follow-up visit and at the end of the follow-up period;
- Practice highly effective contraception during the treatment period (with oral hormonal contraception supplemented by a barrier method, preferably a male condom),
- Practice highly effective contraception for 1 month following the first drug administration on Day 1 (when participants may have received a single dose of MAS825 s.c., which is longer than the guidance for DFV890 for highly effective contraception until 7 days following completion of DFV890 treatment)

Pregnant and/or lactating women are also excluded.

Additionally, WOCBP should avoid becoming pregnant while their male partners are participating in this study. Male participants must agree to abstain from donating sperm and from either any sexual activity with a female partner or to practice highly effective contraception, i.e., barrier protection (condom) with a female partner who is using an intrauterine device (IUD) or hormonal contraception and for at least 90 days following completion of treatment and should not father a child in this period. A condom is required for all sexually active male participants to prevent them from fathering a child AND to prevent delivery of study treatment via seminal fluid to their partner during study treatment and for at least 90 days following completion of treatment.

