- Patients receiving concomitant medications that are known to be strong or moderate inducers of cytochrome CYP2C9 enzyme and/or strong inducers of CYP3A, strong inhibitors of CYP2C9 and/or strong or moderate inhibitors of CYP3A and the treatment cannot be discontinued or switched to a different medication within 5 half-lives or 1 week (whichever is longer) prior to Day 1 and for the duration of the study.

- At screening, pre-malignant clonal cytopenias or clonal cytopenia of unknown significance (CCUS).
- History of ongoing, chronic, or major recurrent infectious disease, at the discretion of the Investigator, at the start of screening.
- Patients with suspected or proven immunocompromised state at screening.
- Use of any biologic drugs targeting the immune system within 26 weeks of Day 1.
- Major non-cardiac surgical or major endoscopic procedures within the past 6 months prior to the start of screening.
- Multi-vessel coronary artery bypass graft (CABG) surgery within the past 3 years prior to the start of screening.
- Planned coronary revascularization (percutaneous coronary intervention (PCI) or CABG) or any other major surgical procedure during the study (until End of Study (EOS)).
- Symptomatic Class IV heart failure (New York Heart Association [NYHA]) at the start of screening.
- Women of childbearing potential, defined as all women physiologically capable of becoming pregnant, **unless** they are using highly effective methods of contraception for at least 3 months prior to first drug administration (Day 1), during dosing and for 5 months after Day 1.

Treatment Groups:

Active treatment: DFV890 administered orally once daily (QD) at various doses (0 mg [matching placebo], 10 mg, 25 mg, 50 mg, 100 mg) over four dosing periods of approximately 3 weeks each, for a total of approximately 12 weeks of treatment or a single s.c.dose (CCI mg) of MAS825 or matching placebo. Randomized to one of five treatment sequences comprised of various doses of DFV890, or a single s.c. dose of MAS825, and/or placebo. Investigational study treatment dose adjustments and/or interruptions are not permitted.

[figure not shown]
Data Monitoring/Other Committee: No

Key words

Coronary heart disease, CHIP, inflammatory marker reduction, NLRP3 inflammasome inhibitor

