5.2 Exclusion criteria

Participants meeting any of the following criteria are not eligible for inclusion in this study.

1. Patients receiving concomitant medications (see list of prohibited drugs, [Section 6.8.2](#)) that are known to be:
 - strong or moderate inducers of CYP2C9 enzyme, or
 - strong inducers of CYP3A, or
 - strong inhibitors of CYP2C9, or
 - strong or moderate inhibitors of CYP3A
 - and the treatment cannot be discontinued or switched to a different medication within 5 half-lives or 1 week (whichever is longer) prior to Day 1 and for the duration of the study.
2. Use of other investigational drugs within 5 half-lives of Day 1, or until the expected PD effect has returned to baseline, whichever is longer.
3. History of hypersensitivity to any of the study treatments or excipients or to drugs of similar chemical classes.

4. History of drug abuse or unhealthy alcohol use within the 12 months prior to the start of screening, per Investigator judgement.
Unhealthy alcohol use may be considered with a history of, or current, alcohol misuse/abuse or "Five or more drinks on the same occasion on each of 5 or more days in the past 30 days." However unhealthy alcohol use may be considered at lower level per investigator judgement based on participant's history.
5. Any diagnosed psychiatric condition that includes, but is not limited to, a history of mania, bipolar disorder, psychotic disorder, schizophrenia, or schizoaffective disorder, depression or anxiety, which may jeopardize patient safety or compliance with study procedures, as judged by the Investigator.
6. WOCBP, defined as all women physiologically capable of becoming pregnant, unless they are using highly effective methods of contraception for at least 3 months prior to first drug administration (Day 1), during dosing and for 5 months after the single s.c.dose administration of MAS825 or placebo dose. Highly effective contraception methods include:
 - Total abstinence from heterosexual intercourse (when this is in line with the preferred and usual lifestyle of the participant). Periodic abstinence (e.g., calendar, ovulation, symptothermal, post-ovulation methods) and withdrawal are not acceptable methods of contraception.

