8.6.4 Pregnancy

- Details of all pregnancies in female participants will be collected after the start of study treatment and until 5 months after the single dose administration of MAS825 or placebo on Day 1. If indicated, details of all pregnancies in female partners of male participants will be collected after the start of study treatment and until 90 days after the end of study drug administration.
- While pregnancy itself is not considered to be an AE or SAE, any pregnancy complication or elective termination of a pregnancy for medical reasons will be reported as an AE or SAE.
- Abnormal pregnancy outcomes (e.g., spontaneous abortion, fetal death, stillbirth, congenital anomalies, ectopic pregnancy) are considered SAEs and will be reported as such.
- Any post study pregnancy-related SAE considered reasonably related to the study treatment by the Investigator will be reported to Novartis as described in [Section 8.6.3](#). While the Investigator is not obligated to actively seek this information in former study participants/pregnant female partner, he or she may learn of an SAE through spontaneous reporting.

Any female participant who becomes pregnant while participating in the study will discontinue study treatment or be withdrawn from the study.

Pregnancies

If a female trial participant becomes pregnant, the study treatment should be stopped, and the pregnancy consent form should be presented to the trial participant. The participant must be given adequate time to read, review and sign the pregnancy consent form. This consent form is necessary to allow the Investigator to collect and report information regarding the pregnancy. To ensure participant safety, each pregnancy occurring after signing the informed consent must be reported to Novartis within 24 hours of learning of its occurrence. The pregnancy should be followed up to determine outcome, including spontaneous or voluntary termination, details of the birth, and the presence or absence of any birth defects, congenital abnormalities, or maternal and/or newborn complications.

Pregnancy should be recorded and reported by the Investigator to Novartis CMO&PS. Pregnancy follow-up should be recorded on the same form and should include an assessment of the possible relationship to the study treatment any pregnancy outcome. Any SAE experienced during pregnancy must be reported.

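### Protocol Section 2.3.1.5 sets contraception durations that contradict the summary and exclusion criterion 6, and its claim that the Day 1 rule is the longer one fails for anyone who completes treatment

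*Protocol*

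**What the plan says.** Section 2.3.1.5 of the Protocol opens by stating that participants must be told of unknown fetal risk and that "they must adhere to the contraception requirements outlined in the exclusion criteria". It then gives its own list, introduced by "WOCBP can be included if they fulfill the following criteria". On duration the list asks for:

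- before the study: "Practice highly effective contraception for at least 1 month prior to screening";
- throughout the treatment period (a separate bullet);
- after dosing: "Practice highly effective contraception for 1 month following the first drug administration on Day 1". The reason given is that the participant may have received MAS825 on that day. The bullet adds "which is longer than the guidance for DFV890 for highly effective contraception until 7 days following completion of DFV890 treatment".

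Three other places give different figures or a different window:

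- Section 1.1, key exclusion criteria: "for at least 3 months prior to first drug administration (Day 1), during dosing and for 5 months after Day 1".
- Section 5.2, exclusion criterion 6: the same three months before Day 1, then "during dosing and for 5 months after the single s.c.dose administration of MAS825 or placebo dose".
- Section 8.6.4, on collecting pregnancies in female participants: "until 5 months after the single dose administration of MAS825 or placebo on Day 1".

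**The concern.** There are two separate problems.

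First, Section 2.3.1.5 disagrees with the summary and criterion 6 on both the pre-treatment and the post-dose duration. It also disagrees with the criteria it tells the reader to follow. Its list is worded as conditions for inclusion, so a reader could take it as complete.

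Second, the comparison in its last bullet does not work for a completer. Participants and investigators are blinded, so the bullet uses a single rule counted from Day 1 to cover both drugs. That is safe only if the Day 1 rule ends later than the DFV890 rule. For a participant who takes about 12 weeks of treatment, it ends earlier.

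What is at stake is participant safety. The same section says that DFV890 has not been studied in reproductive toxicology and that no reproductive toxicity data exist for MAS825. A site or participant relying on Section 2.3.1.5 alone would apply different start and end dates from those in Section 5.2. The post-dose period is the more exposed part. It runs after enrolment, when an eligibility check can no longer catch the error, and under the five-month text it outlasts the planned Day 114 safety call (Section 1.3).

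**Working it through.** **Inputs**

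| Quantity | Value | Source (Protocol) |
|---|---|---|
| Post-dose, first version | 1 month after Day 1 | 2.3.1.5 |
| Post-dose, second version | 5 months after Day 1 | 1.1; 5.2, criterion 6 |
| DFV890 guidance | completion + 7 days | 2.3.1.5 |
| Last planned DFV890 dose | Day 84 | 6.2.3 |
| Permitted dosing-period length | 17 to 35 days, four periods | 6.2.3 |
| Pre-study, first version | 1 month before screening | 2.3.1.5 |
| Pre-study, second version | 3 months before Day 1 | 1.1; 5.2, criterion 6 |
| Screening window | Day -30 to Day -1 | 1.3 |

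Assumption: a month is 30 days. In calendar months, one month after Day 1 falls on Day 29 to 32, and five months after Day 1 falls on Day 151 to 154.

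**The comparison in the last bullet**

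- One month after Day 1: 1 + 30 = Day 31.
- DFV890 rule, on schedule: 84 + 7 = Day 91.
- Difference: 91 − 31 = 60 days. The rule described as longer ends 60 days earlier, and also before the last planned dose.
- All four periods at 17 days: last dose 4 × 17 = Day 68, + 7 = Day 75; 75 − 31 = 44 days earlier.
- All four periods at 35 days: last dose 4 × 35 = Day 140, + 7 = Day 147; 147 − 31 = 116 days earlier.
- The statement becomes true only when last dose + 7 < 31, that is, when the last dose is before Day 24.

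The stated comparison is therefore not reproduced for any completer. With the five-month figure (1 + 150 = Day 151) it would hold in all three cases. That is arithmetic only and does not say which duration is clinically right.

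**The end date a participant would follow**

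The treatment-period bullet means that no completer stops at Day 31 under Section 2.3.1.5. The end date is the last dose, or the last dose + 7 if the DFV890 guidance is added.

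| Case | 2.3.1.5 ends | 1.1 and 5.2 end | Gap |
|---|---|---|---|
| On schedule | Day 84 or 91 | Day 151 | 67 or 60 days |
| Four 17-day periods | Day 68 or 75 | Day 151 | 83 or 76 days |
| Four 35-day periods | Day 140 or 147 | Day 151 | 11 or 4 days |
| Very early stop | Day 31 | Day 151 | 120 days |

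The second and third rows are outer bounds.

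**Before treatment**

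- Section 2.3.1.5: 30 days before a screening visit that is itself 1 to 30 days before Day 1, so 31 to 60 days before Day 1.
- Sections 1.1 and 5.2: 90 days before Day 1.
- Gap: 90 − 60 = 30 to 90 − 31 = 59 days.

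**The case against.** The strongest reply is that the protocol already shows which text governs. Section 2.3.1.5 points to the exclusion criteria, Section 5.2 is the formal list, the summary agrees with it, and Section 8 permits no waivers. A woman who meets criterion 6 also meets every duration in Section 2.3.1.5, so the two can be followed together. This stands, and it is why the enrolment risk is limited. It does not help a reader who has only Section 2.3.1.5, which gives shorter figures without signalling that longer ones apply.

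A second reply is that the comparison is between two intervals, each counted from that compound's own last dose: about 30 days for MAS825 against 7 for DFV890. No sequence combines both active drugs (Section 4.1), and on that reading the sentence is true. The reading is possible but weaker. The bullet gives an end point tied to completing DFV890, and it uses the Day 1 rule to cover participants who do not know which drug they received. If this reading is accepted, the contradiction in durations remains.

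Two smaller points also stand. The ranges from 17- and 35-day periods are extremes, since 35 days is allowed only when a visit cannot be scheduled within its window. With the ±2-day end-of-treatment window, the last dose falls on about Day 82 to 86 and the completer gap is about 58 to 69 days (151 − 93 to 151 − 82). And Section 8.6.4 is a data-collection window, not a contraception rule; it matters here only because it should stay aligned with the post-dose period chosen.

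**Conclusion.** The point holds. Section 2.3.1.5 contradicts Section 1.1 and exclusion criterion 6 on both the pre-treatment and the post-dose duration. Its comparison with the DFV890 rule is wrong for any participant who completes treatment, unless each interval is read from its own compound's last dose.

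For an on-schedule completer the end dates differ by 60 to 67 days; for a very early stop the difference is about 120 days. The start dates differ by 30 to 59 days. These figures assume 30-day months; calendar months move the five-month date by at most three days. The number of women affected cannot be estimated, because the documents do not say how many women of childbearing potential are expected and the consent form was not available.

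This should be fixed, as a safety-text correction. It has no bearing on power, type I error or the analysis, and this review takes no position on which duration is clinically right.

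**What to change.** Reconcile Protocol Sections 1.1, 2.3.1.5, 5.2 (criterion 6) and 8.6.4 so that the contraception text gives one pre-treatment and one post-dose duration, with the pregnancy-collection window in 8.6.4 aligned to the latter. The sponsor chooses the durations. In Section 2.3.1.5, either replace the list with a cross-reference to criterion 6 or make its figures match, and correct or delete the comparison with the DFV890 guidance. If the comparison is kept, state the day from which each interval is counted. Check that the consent form carries the same durations.

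The cost is a text correction, by amendment or clarification letter, plus the consent-form check. Sample size, visit schedule and statistical analysis do not change.
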